## **Statistical analysis plan**

We will compare infant outcomes between children exposed to the intervention and those in control communities. We will use logistic regression to compare dichotomous outcomes (e.g., exclusive breastfeeding through 6 months, completion of vaccinations, infant hospitalization) and linear regression for continuous outcomes (e.g., mid-upper arm circumference). Primary outcomes will be evaluated using an intention-to-treat analysis without adjustment for other covariates. We will account for correlation within church communities by adjusting the variance for the effect of clustering.

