**Methods:** The study utilizes a community-randomized trial design in which 11 communities will be randomized to receive the intervention and 11 communities will be randomized as control communities. The unit of randomization at the house of worship. The target population for this undertaking is pregnant women and women who recently delivered in rural communities in the North Gondar region of Ethiopia. Infants enrolled in the study will have a baseline evaluation within 10 days of birth and the primary outcomes of mid-upper arm circumference (MUAC) and exclusive breastfeeding will be measured at a follow-up visit at between 5 and 6 months after birth. The sample size of 150 infants from intervention churches and 150 infants from control churches is based on identifying a statistically significant difference of  $\geq 0.2$  cm in mid-upper arm circumference (MUAC) with 80% power at  $\alpha=0.05$ , anticipating 20% of participants being lost to follow-up. We will also have 80% power to detect a significant difference of 50% exclusive breastfeeding at 5-months in the control group versus 70% in the intervention group.

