## Methods:

### Study Design:

In collaboration with the woreda administrative office and the woreda diocese of the EOC, all the kebeles and EOC churches in the woreda will be mapped by the study team and randomly assigned to intervention or control. Sites will be selected in a way that ensures they are reasonably far apart in order to avoid contamination. Newborn-mother pairs in the catchment areas of the intervention churches will receive the intervention, whereas those in the control churches will receive routine community health packages implemented by community health workers (HEWs and HDAs).

The intervention will be implemented at the community level by pairs of trained EOC priests and members of the HDA. A list of priests serving at the EOC churches in the intervention arm will be obtained through the woreda diocese and their respective churches. All the priests will be contacted through the church leadership and asked to participate in the study intervention. The intervention will be implemented in collaboration with HDA members recruited by HEWs under the health centers in the catchment areas of the intervention churches. HDA members 55 years old or younger will be asked to participate.

An initial 5-day training will be given to priests and HDA members. The training will focus on newborn health topics including early initiation of and exclusive breastfeeding, maternal nutrition, immunization, childhood illnesses, child health care services, etc. At the end of the training action plans will be prepared by the training organizers, priests, and HDA. Priest will be asked to integrate health messages

---

 Central Statistical Agency - CSA/Ethiopia and ICF. 2017. Ethiopia Demographic and Health Survey 2016. Addis Ababa, Ethiopia: CSA and ICF. Available at <http://dhsprogram.com/pubs/pdf/FR328/FR328.pdf>.

and education into their routine family visits around the birth of a child in structured intervals as culturally appropriate.

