### **Data Collection**

The UoG study team will conduct regular visits in both the intervention and control communities to screen, consent, and register new newborn-mother pairs reported by HEWs, collect baseline data from them, arrange follow-up visit schedules, and collect follow-up data from previously enrolled study participants. Each newborn-mother pair will receive up to three visits by the study team in the sixth month period. The study team will use OpenDataKit (ODK), an electronic data collection system to record data on tablets. The study team will upload the collected data to a secured central web-based server upon return to the UoG campus. The overall processes of recruitment and subsequent data collection activities will be supervised by an on-site study manager. The study team will rely heavily on pre-designed standard operating procedures that contain detailed, step-by-step instructions for collecting and handling data.

The following primary and secondary outcome variables will be assessed in this study:

**Primary outcome variables:** mid-upper arm circumference (MUAC), proportion of mothers exclusive breastfeeding

**Secondary outcome variables:** immunization status (complete vaccination and individual vaccines), frequency of acute illnesses, and frequency of hospitalization

**Predictors (other than intervention):** maternal age, sex of child, maternal education, family economic status, family size, etc.

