**Number of Subjects:**

Group name/description	Desired number of individuals (or other subject unit) who will complete the research
Newborn/Mother Pairs	240

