**Procedures:**

The intervention in this study is intimately tied to the cultural customs and values of the North Gondar region of Ethiopia. In this region, religious leaders of the Orthodox Church have the potential to be strong advocates or hindrances to effort to improve public health and this study aims to explore how linking religious leaders to frontline health workers may catalyze and empower local communities to improve health outcomes for newborns. The study engages several experienced Ethiopian investigators and will seek continual input from a Steering Committee of community members in Gondar to ensure that all elements of the study are culturally appropriate and conducive to the local context.

Newborn-mother pairs will be recruited within the first 10 days after delivery as reported to the study team by Health Extension Workers (HEWs) engaged in the study. Recruitment will start one month following the start of the intervention and all reported newborn-mother pairs who meet the screening criteria will be included in the study until the calculated sample sizes are reached. HEW's routine registers of new deliveries will be used to trace, recruit and screen study participants. Newborn-mother pairs who fulfill an initial screening criteria will be reported to the study team at the University of Gondar (UoG) who will travel to the study site regularly for recruitment of study participants and data collection. Newborn-mother pairs will be reported to the UoG study team both through phone calls made by HEWs and in-person at the time of regular onsite visits by the team.

Eligible newborn-mother pairs will be visited by a member of the study team at their home or at an appointed meeting location in their community to complete the verbal informed consent process. Those pairs who attend church at a parish that received the intervention will be assigned to the intervention arm, and those from the parishes where no intervention was conducted will be assigned to the control arm. Initial baseline data will then be collected and follow-up visit schedules arranged with the study team.

The following materials will be used during the recruitment of study participants:

- Oral consent scripts (see attached scripts) will be used to provide information about the study to potential subjects.
- A checklist of the initial screening criteria will be used by the HEWs and study team to identify appropriate newborn-mother pairs.

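### Optional improvement: the unadjusted primary MUAC analysis is valid, but it passes up about 1 to 2 points of power that adjusting for infant sex could add at almost no cost.

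*Combined protocol and SAP*

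**What the plan says.** The Statistical analysis plan section assigns linear regression to continuous outcomes, with MUAC as the example, and then states: "Primary outcomes will be evaluated using an intention-to-treat analysis without adjustment for other covariates". It continues: "We will account for correlation within church communities by adjusting the variance for the effect of clustering". It describes no adjusted, supportive or sensitivity model, and neither does any other section.

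The Data Collection section lists predictors other than the intervention: "maternal age, sex of child, maternal education, family economic status, family size, etc". The questionnaire described under Data Sources collects socio-demographic variables. No section says what the predictors are for.

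The Study Design section says that kebeles and churches "will be mapped by the study team and randomly assigned to intervention or control", and it mentions no stratification or balancing. The Summary gives 11 communities per arm and 150 infants per arm for a MUAC difference of 0.2 cm with 80% power, "anticipating 20% of participants being lost to follow-up". Number of Subjects gives 240 pairs completing.

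**The concern.** MUAC set the sample size, and the target difference of 0.2 cm is small. In an unadjusted linear model, any variation in MUAC explained by infant sex stays in the error term and widens the interval. Sex is fixed before the intervention can act, is already to be recorded, and can enter a linear model without changing what the treatment coefficient estimates. What is at stake is a slightly less precise primary estimate. Bias and type I error are not in question.

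**Working it through.** **The plan's own figures.** 150 × (1 − 0.20) = 120 per arm, or 240 in total, which agrees with Number of Subjects. The MUAC sample size cannot be reproduced, because no SD or ICC is stated. Solving for the SD with 120 per arm, two-sided 0.05 and no clustering gives 0.2 / [(1.960 + 0.842) × √(2/120)] = 0.553 cm. This is why 0.55 cm is used below.

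**Assumptions, none of them in the documents.** SD 0.55 cm; ICC 0.02 to 0.05; sex difference in MUAC d = 0.2 to 0.3 cm; two-sided test. For an even split of boys and girls the correlation of sex with MUAC is r = d/(2 × SD): 0.2/1.10 = 0.18 and 0.3/1.10 = 0.27. A value of r = 0.30 is added as an upper case.

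**Closed form.** The covariate is allowed to reduce only the within-church variance:

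SE² = 2 × SD² × [ICC/11 + (1 − ICC)(1 − r²)/120]

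Power for 0.2 cm is from the noncentral t with 20 df (22 churches less 2).

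| ICC | r | SE (cm) | Power | Gain (points) |
|---|---|---|---|---|
| 0.02 | 0 | 0.0777 | 68.7% | – |
| 0.02 | 0.18 | 0.0767 | 69.9% | 1.2 |
| 0.02 | 0.27 | 0.0754 | 71.4% | 2.7 |
| 0.02 | 0.30 | 0.0748 | 72.0% | 3.3 |
| 0.05 | 0 | 0.0868 | 59.2% | – |
| 0.05 | 0.18 | 0.0859 | 60.1% | 0.9 |
| 0.05 | 0.27 | 0.0848 | 61.2% | 2.0 |
| 0.05 | 0.30 | 0.0843 | 61.7% | 2.5 |

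With SD 0.50 cm, moving r from 0 to 0.30 raises power from 76.8% to 79.9% at ICC 0.02 and from 67.4% to 69.9% at ICC 0.05. The gain is of the same order.

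In interval terms, at ICC 0.02 and r = 0.27 the 95% half-width falls from 2.086 × 0.0777 = 0.162 cm to 2.086 × 0.0754 = 0.157 cm.

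**Simulation.** 22 churches, 240 infants, cluster-robust variance with t on 20 df, 20,000 runs per cell. The adjusted model holds sex, maternal age and maternal education, with the two maternal effects set to zero.

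| ICC | Sex difference | Unadjusted | Adjusted | Change (points) |
|---|---|---|---|---|
| 0.02 | none | 70.4% | 70.0% | −0.4 |
| 0.02 | 0.2 cm | 69.9% | 70.8% | +0.9 |
| 0.02 | 0.3 cm | 70.4% | 72.7% | +2.3 |
| 0.05 | none | 60.9% | 60.7% | −0.2 |
| 0.05 | 0.2 cm | 61.4% | 62.0% | +0.6 |
| 0.05 | 0.3 cm | 60.9% | 63.1% | +2.2 |

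The Monte Carlo standard error of each power figure is about √(0.7 × 0.3/20,000) = 0.3 points, so the smaller changes are only roughly determined. A separate simulation put the gain at about 1 to 2 points and the loss with uninformative covariates at up to about 0.7. Type I error was 5.3% to 5.6% unadjusted and 5.4% to 5.9% adjusted. All the simulated gain comes from sex.

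**Chance imbalance in sex.** The SD of the between-arm difference in the share of boys is √(2 × 0.25/120) = 6.5 points, ignoring clustering. A 10-point difference (1.55 SDs) shifts the estimate by 0.10 × 0.2 to 0.10 × 0.3 = 0.02 to 0.03 cm. Divided by 0.0777, that is 0.26 to 0.39 of a standard error.

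**The case against.** The strongest reply is that there is no defect. The plan makes an explicit, prespecified and valid choice, the gain is about 2 points or less in the simulation, and every input to that gain is assumed. The two primary outcomes would also follow different adjustment rules. All of this stands, and it is why the point is optional. It does not remove the case for a change that needs no new data and, in the simulation, left type I error about the same.

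A reader might infer more than the documents support:

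- *That the predictor list leaves the primary analysis open to choice after the data are seen.* It does not. The plan specifies no covariates for the primary outcomes, which settles the matter. Any freedom left concerns secondary models that are not described.
- *That adjustment is needed because 22 churches are randomised without described balancing.* The unadjusted interval already allows for chance imbalance. Infant sex is an individual factor with no evident reason to differ by church, so adjusting for it would not correct imbalance between churches.
- *That the gain is as large as 4 points.* That figure appears if clustering is ignored and the covariates are taken to explain 10% of the variance (80% to 84.0%). With clustering as in the table above, the maximum is 3.3.
- *That maternal age and education add precision.* No figure here shows it.

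**Conclusion.** The point holds as a cheap, optional improvement. Under SD 0.55 cm, ICC 0.02 to 0.05 and a sex difference of 0.2 to 0.3 cm, adjusting the primary MUAC model adds about 1 to 2 points of power. The closed-form upper case, r = 0.30, gives about 3. If the covariates carry nothing, up to about 0.7 points are lost. The facts about the plan are certain, but the size rests wholly on these assumptions. The unstated SD and ICC matter far more to the trial's power: the same table shows a fall from 68.7% to 59.2% between ICC 0.02 and 0.05 without adjustment. The unadjusted analysis should not be read as wrong or biased.

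**What to change.** In the Statistical analysis plan section, define the primary MUAC model as a linear regression on randomised arm plus infant sex, named before data are seen, with the clustering adjustment already planned. Report the unadjusted estimate beside it. Maternal age and maternal education may be added to the named list, on the understanding that no gain from them has been shown.

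Keep newborn size out of this model. Outreach starts in the last month of pregnancy and enrolment comes after birth, so the intervention could already have affected it. Age at measurement depends on visits scheduled after allocation, so it belongs in a supportive model if it is used at all. Leave the exclusive breastfeeding analysis unadjusted, because adding covariates to a logistic model changes the odds ratio being estimated.

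The cost is two or three sentences and one to a few degrees of freedom. No new data are needed. The downside is the small loss of power given above if the covariates turn out to be uninformative.

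### No small-sample correction or degrees of freedom is named for 22 randomised churches; a standard cluster-robust variance would test both primary outcomes at about 5.5–8% instead of 5%

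*Combined protocol and SAP*

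**What the plan says.** In the Summary (Methods), "11 communities will be randomized to receive the intervention and 11 communities will be randomized as control communities", and "The unit of randomization at the house of worship". The target is "The sample size of 150 infants from intervention churches and 150 infants from control churches", with 20% loss to follow-up allowed for. The Number of Subjects table gives 240 pairs under the column "Desired number of individuals (or other subject unit) who will complete the research".

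The Statistical analysis plan uses linear regression for continuous outcomes and logistic regression for binary ones. On the primary analysis it says "Primary outcomes will be evaluated using an intention-to-treat analysis without adjustment for other covariates". On clustering it says only "We will account for correlation within church communities by adjusting the variance for the effect of clustering". No section adds an estimator, a finite-sample correction, a reference distribution or degrees of freedom, and no separate analysis plan is referred to.

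On church sizes, Procedures says that "all reported newborn-mother pairs who meet the screening criteria will be included in the study until the calculated sample sizes are reached". No number per church is set.

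**The concern.** With 11 clusters per arm, the large-sample theory behind ordinary cluster-robust standard errors does not yet hold well. The uncorrected variance is biased downwards, and a normal reference ignores the fact that the variance is estimated from about 20 degrees of freedom. Both errors push in the same direction.

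Ordinary regression with cluster-robust standard errors fits the plan's sentence as written. If that is what is run, the confidence intervals for both primary outcomes are too narrow and the 5% test is not a 5% test. Leaving the method open also allows it to be chosen after the results are known, and in a borderline case the choice could decide significance.

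**Working it through.** **Inputs from the documents.** 11 + 11 churches; α = 0.05 (sidedness not stated, two-sided assumed); 150 infants per arm with 20% loss, so 300 × 0.8 = 240 completers. This reproduces the Number of Subjects table: 120 per arm, or 120/11 = 10.9 per church. The intracluster correlation (ICC) and church sizes are not given.

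**Step 1: equal church sizes, normal outcome. This holds for any ICC.** Let s² be the pooled variance of church means within arms, on 20 df. The unbiased variance of the arm difference is 2s²/11. The uncorrected robust variance is (SS₁ + SS₂)/11² = 20s²/121 = (10/11) × 2s²/11. Each version therefore rejects when |t₂₀| exceeds its critical value times the square root of its variance ratio:

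| Version | Variance ratio | Threshold on t₂₀ | Null rejection |
|---|---|---|---|
| Uncorrected, normal | 10/11 | 1.960 × √(10/11) = 1.869 | 7.6% |
| 22/21 factor, normal | 10/11 × 22/21 = 20/21 | 1.960 × √(20/21) = 1.913 | 7.0% |
| 22/21 factor, t(20) | 20/21 | 2.086 × √(20/21) = 2.036 | 5.5% |
| CR2, t(20) | 1 | 2.086 | 5.0% |
| CR3, t(20) | 11/10 | 2.086 × √1.1 = 2.188 | 4.1% |

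CR2 and CR3 scale each church's residual sum by (1 − h)^−½ and (1 − h)^−1. In an arm-only model h is the church's share of its arm, here 1/11.

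**Step 2: size variation by chance alone.** With no quota and equal expected births per church, the coefficient of variation (CV) of church size is √[(1 − 1/11)/(120/11)] = 0.29.

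**Step 3: simulated null rejection at chance-only sizes.** Unless noted, these are 100,000 trials per scenario at assumed ICC 0.02–0.10, covering a normal outcome and a binary outcome at 50% prevalence:

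- Uncorrected, normal: 7.6–8.0%. A separate set of 10,000 runs per scenario at ICC 0.01–0.10 gave 7.9–8.3%.
- 22/21 factor, normal: 7.3–7.6%, or 7.0–7.3% on the logit scale (10,000-run set).
- 22/21 factor, t(20): 5.4–5.8%.
- Design effect from the estimated ICC: 5.0–6.4% (normal), 3.8–5.0% (t(20)).
- Random intercept, arm circumference only: 5.2–6.3% (normal), 4.0–4.9% (t(20)).
- CR2 with Satterthwaite df: 4.7–5.0%.
- CR3 with t(20): 3.8–4.1%.

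**Step 4: more unequal churches (assumed).** The uncorrected version with a normal reference gives 8.1–8.8% at CV 0.5, 9.4–10.6% at CV 0.8 and 10.2–12.4% at CV 0.92. CR2 with Satterthwaite df gives 4.8–5.3% at CV 0.5 and 4.9–5.7% at CV 0.8. The t test on church means (20 df) stayed at 4.3–5.4% in every scenario of the 10,000-run set, which went up to CV 0.92.

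**Step 5: interval width, CR2 against the alternatives.** At equal sizes it is √1.1 × 2.086/1.960 = 1.116 times the uncorrected normal-reference width, and √(21/20) = 1.025 times the width with the 22/21 factor and t(20). At chance-only sizes, simulation gives about 13% and 3.5% wider respectively.

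**The case against.** The plan does commit to accounting for church-level correlation, and a competent analyst could meet that commitment soundly. A design effect or a random intercept with t on 20 df already holds about 5% or less. Even the 22/21 factor with t(20) is off by less than one percentage point at chance-only sizes, where CR2 would widen intervals by only about 3.5%. On this view the gap is one of specification, not a demonstrated error. That much stands: nothing in the documents shows which method is intended.

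A reader might go further and infer that the trial's type I error is inflated, perhaps to 10% or more. The documents do not support that. Such rates need the uncorrected variance, a normal reference and very unequal churches together, and neither church sizes nor an ICC is given. Nor is 10% a ceiling, since 12.4% appeared at an assumed CV of 0.92. No single upper figure describes this trial.

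Choosing among the sound methods is also partly a matter of judgement. CR2 with Satterthwaite df is itself slightly liberal at CV 0.8 (up to 5.7%), while the church-mean t test holds its level but can lose power. The Satterthwaite df formula was checked by direct computation for the linear model only, although the simulated rejection rates cover both outcomes.

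The objection does not remove the point that the sentence equally admits versions with a true rate of 7–8%, and that nothing prevents the choice being made after the data are seen.

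**Conclusion.** The point holds as a conditional one. The plan leaves the small-sample treatment of 22 churches open, and a standard cluster-robust variance, which its wording permits, would make both primary tests liberal. The firmest figures are the closed-form ones: 7.6%, 7.0% or 5.5% depending on the version. They assume equal church sizes, a normal outcome and a two-sided test, but no ICC. The 7–8% for normal-reference versions at chance-only sizes also rests on assumed ICCs of 0.01–0.10. Anything higher depends on an assumed inequality of church sizes. The omission itself is certain and its effect moderate. It should be corrected before analysis.

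**What to change.** Add to the Statistical analysis plan: *Tests and confidence intervals for the arm effect on both primary outcomes will use a cluster-robust variance with church as the cluster, the CR2 correction, and a t reference with Satterthwaite degrees of freedom.* CR3 with t on 20 df, or a church-level t test with 20 df, is also acceptable, provided one method is named in advance as primary.

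The cost is one sentence and a few lines of code, with no new data. There is some loss of nominal power, part of which was only excess type I error under the uncorrected version. At chance-only sizes, power with CR2-Satterthwaite against the uncorrected normal-reference version, at assumed ICC 0.02 / 0.05 / 0.10, is:

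- Breastfeeding, 50% v 70%: 77 v 84%, 67 v 75%, 53 v 63%.
- Arm circumference, 0.2 cm: 67 v 75%, 57 v 66%, 46 v 55%. The plan gives no standard deviation, so this uses the one its sample size implies without clustering: 0.2/[(1.960 + 0.842) × √(2/120)] = 0.553 cm.

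CR3 costs about 3–4 further points. The church-level t test costs more if churches are very unequal: for arm circumference at CV 0.8 its power is 47 / 42% at ICC 0.02 / 0.05, against 62 / 51% for CR2-Satterthwaite.
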